#### 15.5. PRINCIPAL INVESTIGATOR/SPONSOR SAFETY REVIEW

The investigator will ensure that the protocol and consent form are reviewed and approved by the appropriate Institutional Review Board/Independent Ethics Committee (IRB/IEC) prior to the start of any study procedures. The IRB/IEC will be appropriately constituted and will perform its functions in accordance with US Food and Drug Administration (FDA) regulations, International Conference on Harmonization (ICH) Good Clinical Practice (GCP) guidelines, and local requirements as applicable.

The investigator(s) undertake(s) to perform the study in accordance with this protocol, Good Clinical Practice (GCP), and the applicable regulatory requirements. The Investigator is required to ensure compliance with the investigational product administration schedule, visits schedule and procedures required by the protocol. The investigator agrees to provide all information requested in the CRF in an accurate and legible manner according to the instructions and to provide the Sponsor representatives direct access to source documents.

The Principal Investigator will be responsible for monitoring the safety and efficacy of the trial, executing the Data Safety Monitoring (DSM) plan, and complying with all reporting requirements to the Sponsor, local and federal authorities.

#### **15.6.** DATA SAFETY MONITORING BOARD

A Data Safety Monitoring Board (DSMB) will be established with a primary function to protect the safety and welfare of study subjects. The DSMB will meet to examine Protocol Date: December 23, 2014 Amendment Date: September 12, 2017 Page 71 of 94

comprehensive safety data, which will be provided to the DSMB at regular intervals (quarterly) as defined by their charter, but may meet with greater frequency at their discretion. DSMB members will receive automatic electronic notification as soon as an SAE is reported at the study site. The DSMB members will have access to needed subject clinical data for complete documentation of all SAEs. All pertinent safety data including information on deaths, tumor progressions, adverse events and laboratory safety data will be reviewed. Subsequent to each meeting of the DSMB, the members will recommend in writing to the Sponsor that either the study continue in its current form, undergo protocol modification to deal with a critical emerging issue, or be stopped because of safety concerns. DSMB meetings will consist of an open session, which the Sponsor's representatives can attend, and a confidential closed session, which the Sponsor is representatives cannot attend. Minutes will be kept for both, the open and closed sessions of the DSMB meetings. The minutes of the closed sessions will not be revealed to the Sponsor until the study has been completed and the database has been locked.

#### **15.7.** STOPPING RULES

An external DSMB will oversee this study. The investigators and representatives of the Sponsor and DSMB will review and discuss subject data for all subjects enrolled by teleconference. The DSMB could recommend stopping the clinical trial for safety purposes.

The development of dose limiting toxicity (DLT) in any subject will prompt a review of safety data by DSMB. The development of any DLT toxicity in  $\geq 33\%$  of the accumulated number of subjects at any dosing during the assessment period (28 days after last booster infusion) will result in protocol discontinuation. However, if DTLs only occur in the Activation or Booster phase, then a decision by DSMB may be made to continue enrolling subjects to receive only priming and in-situ vaccination phases.

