The development of any Grade 4 or greater toxicity in any subject at any time will prompt a review of safety data by the Sponsor, PI and the DSMB prior to accrual of any additional subjects. It is recognized that Grade 4 events and death can occur in this population due to disease progression. Therefore, dosing will continue for currently enrolled subjects at the occurrence of a grade 4 event according to protocol unless the PI determines the Grade 4 or greater event is definitely or probably related to the study drug. If attribution is assigned to the study drug dosing will be suspended pending review by the DSMB.

In accordance with the 3+3 design, three subjects will be accrued into the first dosing schedule. If during the priming, vaccination and activation steps no ADLT are observed in any of the three subjects, accrual into the next cohort is allowed. If an ADLT occurs in two of the three subjects, no further dose frequency escalation is allowed. If ADLT occurs in one of

the three subjects, three additional subjects will be accrued into the same cohort. If no ADLT occurs within the additional three subjects, accrual into the next cohort can begin. If an ADLT is observed in any of the additional three subjects, no further dose escalation is permitted.

The development of any DLT toxicity in  $\geq$  33% of the accumulated number of subjects in any and all dosing schedules during the Safety Evaluation Period will result in protocol discontinuation.

At the completion of the Safety Evaluation Period for all cohorts, the safety evaluation of Part 1 will be considered completed and all enrollment will be closed. Efficacy evaluation will continue monthly for each subject until death or loss to follow-up.

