In the cohort without cryoablation, the IV AlloStim® infusion and subsequent rejection is expected to cause release of inflammatory cytokines that will activate NK cells and memory T-cells and cause them to traffic to metastatic tumor lesions, creating an in-situ vaccination step intended to create anti-tumor specific immunity. Tumor vaccines generally contain a source of tumor antigen combined with an adjuvant which promotes immune recognition and primes for development of a specific immune response against the tumor antigen. In these schedules, a source of tumor antigen is created in-vivo by AlloStim® leading to the release of internal antigens. These factors are expected to serve as an adjuvant by promoting maturation of DC to prime for anti-tumor specific Th1 immunity.

3. Activation phase:

Intravenous infusions of AlloStim® are designed to create a "cytokine storm" of inflammatory cytokines capable of suppressing the ability of tumors to evade immune responsiveness. In addition, intravenous AlloStim® has been shown to activate host T-

cells and macrophages through CD40L-CD40 interaction and cause these activated cells to extravasate to the tissues. Since priming and vaccination are expected to increase the titer of circulating Type 1 memory cells, extravasation causes an increase in immune cell infiltration at sites of inflammation, including metastatic tumor sites. This provides a mean to maintain and support an active cellular immune response against widely disseminated tumors. However, the inflammation is non-specific such that any inflammatory lesion such as arthritic lesions, inflammatory bowel or sites of previous injury can also become inflamed or the existing inflammation becomes exacerbated.

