# Dosing Schedule A-2: Intradermal and Intravenous Dosing With AlloStim® alone

The priming step: Subjects will receive an ID injection of AlloStim® (0.5 ml) on Days 0, 3, 7, 10 and 14.

The vaccination step: Subjects will receive IV AlloStim® (3 ml) on Day 21.

The activation step: Subjects will receive an IV infusion of AlloStim® (3ml) on Day 28.

The booster step: Subjects will receive two IV booster infusions of AlloStim® (3ml), one on Day 49 and another on Day 77.

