# **Toxicity Monitoring**

Two types of toxicity are assessed for determination of whether a Dose Limiting Toxicity (DLT) has occurred. An acute dose limiting toxicity (ADLT) is assessed within 48h of a dose administration during the priming, vaccination and activation steps of each protocol. Cumulative dose limiting toxicity (CDLT) is assessed during the complete Safety Evaluation Period including any ADLT that occurs in the booster dosing.

An ADLT is defined as the occurrence of any of the following within 48h of dosing:

- Any  $\geq$  Grade 3 local injection site reaction;
- Any  $\geq$  Grade 3 graft vs host disease;
- Any  $\geq$  Grade 3 infusion related symptoms of duration > 2 days;
- Any  $\geq$  Grade 4 infusion reaction of any duration

For any Grade 1-2 acute toxicity, the study drug administration schedule can continue to the next scheduled dose. If an ADLT is observed, the subject will be followed until the toxicity is resolved or the subject is stable. No further dosing for that subject will occur after an ADLT event

A CDLT event is defined as the occurrence of any of the following within the Safety Evaluation Period

- Any  $\geq$  Grade 3 graft vs. host disease
- Any toxicity  $\geq$  Grade 3 that is probably or definitely related to the study drug;
- Any toxicity not present at baseline that occurs at  $\geq$  Grade 4
- Any autoimmune toxicity  $\geq$  Grade 3 not present at baseline

All adverse events (AEs) and serious adverse events (SAEs), regardless of attribution to the study drug, will be coded, graded and become part of the final safety report for each cohort. The DSMB will review the safety data on each cohort and recommend whether to advance enrollment to the next cohort.

The development of any Grade 4 or greater toxicity in any subject at any time will prompt a review of safety data by the Sponsor, PI and the DSMB prior to accrual of any additional subjects. It is recognized that Grade 4 events and death can occur in this population due to disease progression. Therefore, dosing will continue for currently enrolled subjects at the occurrence of a grade 4 event according to protocol unless the PI determines the event is definitely or probably related to the study drug. If attribution is assigned to the study drug dosing will be suspended pending review by DSMB.

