In accordance with the 3+3 design, three subjects will be accrued into the first dosing schedule. If during the priming, vaccination and activation steps no ADLT are observed in any of the three subjects, accrual into the next cohort is allowed. If an ADLT occurs in two of the three subjects, no further dosing is allowed. If ADLT occurs in one of the three subjects, three additional subjects will be accrued into the same cohort. If no ADLT occurs within the additional three subjects, accrual into the next cohort can begin. If an ADLT is observed in any of the additional three subjects, no further dose escalation is permitted.

The development of any DLT toxicity in  $\geq$  33% of the accumulated number of subjects in any and all dosing schedules during the Safety Evaluation Period will result in protocol discontinuation.

At the completion of the Safety Evaluation Period for all cohorts, the safety evaluation of Part 1 will be considered completed and all enrollment will be closed. Efficacy evaluation will continue monthly for each subject until death or loss to follow-up.

# Part 2

The safety and efficacy data from Part 1 will be evaluated and the favored schedule advanced to Part 2. In Part 2 of the trial, up to 25 additional subjects may be accrued.

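### The DLT stopping rules contradict each other: the 33% stop cancels the 1-of-3 expansion, Sections 3 and 8 differ at 2 of 3, and the Section 15.7 exception appears nowhere else

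*Combined protocol and SAP*

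**What the plan says.** Two rules act on the same events.

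**The 33% rule.** Sections 3 and 8 use the same sentence: DLTs in at least 33% "of the accumulated number of subjects in any and all dosing schedules during the Safety Evaluation Period will result in protocol discontinuation". Neither section gives a minimum number of subjects or an exception. Section 15.7 repeats the threshold and the consequence. It then adds that, where DLTs occur only in the activation or booster phase, "a decision by DSMB may be made to continue enrolling subjects to receive only priming and in-situ vaccination phases".

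**The 3+3 rule for acute DLTs.** Section 8 (Toxicity Monitoring) says ADLT is "assessed within 48h of a dose administration during the priming, vaccination and activation steps of each protocol". It presents ADLT as one of the two kinds of toxicity that make up a DLT. For one event among the first three subjects, Section 8 says: "If ADLT occurs in one of the three subjects, three additional subjects will be accrued into the same cohort". Section 3 has the same provision. For two events, the sections differ:

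- Section 3: "If an ADLT occurs in two of the three subjects, no further dose frequency escalation is allowed".
- Section 8: "If an ADLT occurs in two of the three subjects, no further dosing is allowed".

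Both sections say that an ADLT among the three added subjects ends dose escalation. No text says which rule takes precedence.

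**The concern.** A stopping rule is written in advance so that its consequence is not chosen after the toxicity has been seen. Here the first ADLT in the first cohort meets two instructions that cannot both be followed: close the protocol, or accrue three more subjects on the same schedule. If that event occurred at the Day 28 activation dose, Section 15.7 offers a third course, continued enrolment on a shortened regimen at the DSMB's discretion.

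The number of subjects exposed after an early signal, and the regimen they receive, would then depend on which paragraph is cited.

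**Working it through.** The plan has no calculation to reproduce. The 33% threshold is stated without derivation, and Section 16.1.8 simply asserts that at least three subjects per schedule are enough. The check compares d/n with 0.33 and sets the written consequences side by side.

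**Inputs**

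- Threshold: DLTs in at least 33% of accumulated subjects, all schedules together (Sections 3 and 8).
- Part 1: three subjects in A-1 and three in A-2. Part 2: up to 25 more (Section 8). Maximum 3 + 3 + 25 = 31.
- An ADLT is a DLT, and its window covers priming, vaccination and activation (Section 8).
- The Safety Evaluation Period runs through dosing and until 28 days after the last dose (Section 3), so an ADLT falls inside the period over which the 33% is counted.

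**Shares**

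- 1/3 = 33.3%: met
- 2/3 = 66.7%: met
- 1/6 = 16.7%: not met
- 2/6 = 33.3%: met
- 10/31 = 32.3%: not met; 11/31 = 35.5%: met

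The fewest DLTs that trigger the stop are therefore 1 of 3, 2 of 6, 3 of 9 and 11 of 31.

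**Written consequences for the first cohort**

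| Data | 33% rule, Sections 3 and 8 | ADLT rule | Section 15.7, only if every DLT was in activation or booster |
|---|---|---|---|
| 1 of 3 | discontinue | add three subjects | DSMB may continue, shortened regimen |
| 2 of 3 | discontinue | Section 3: no escalation of dose frequency; Section 8: no dosing | DSMB may continue, shortened regimen |
| 1 of 6 after expansion | not met | open next cohort | not reached |
| 2 of 6 after expansion | discontinue | no further escalation | DSMB may continue, shortened regimen |

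**Reading the table**

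1. *1 of 3.* Discontinuing and accruing three more exclude each other. The third and fourth rows can be reached from 1 of 3 only if the 33% rule was not applied at three subjects. Applied literally, the expansion never operates in the first cohort. This does not depend on the phase in which the ADLT occurred.
2. *2 of 3.* Discontinuation satisfies both versions of the ADLT rule, but the versions are not equivalent. Once the 33% rule is held back at small numbers, or the exception is used, it matters whether dosing or only escalation is barred.
3. *Section 15.7.* If both ADLTs of a 2-of-3 result occurred at activation, Section 8 bars further dosing while Section 15.7 lets the DSMB continue priming and vaccination. If any DLT occurred in priming or vaccination, the exception does not apply and Section 15.7 agrees with Sections 3 and 8 on the 33% stop.

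**The case against.** **Section 15.7 is the dedicated stopping section, so its exception qualifies the general rule.** That is a natural reading and may well be the intent. The protocol does not say so, and Sections 3 and 8 do not point to Section 15.7. Even if it is accepted, the 1-of-3 conflict and the 2-of-3 difference remain, because both arise within Sections 3 and 8.

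**The 33% may be meant as an end-of-period count, taken after any expansion.** One ADLT would then be 1/6 = 16.7% and the rules would fit together. This is probably the sensible intent, and the fix below adopts it in substance. But the text counts any DLT among accumulated subjects and states neither a minimum number nor a time of assessment.

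**Other safeguards exist.** This stands. Any DLT prompts DSMB review (Section 15.7). Any toxicity of Grade 4 or above prompts review before further accrual, a subject with an ADLT receives no more drug, and the DSMB reviews each cohort before the next opens (Section 8). Subjects are not left unprotected; what is undetermined is the consequence of the rule. The DSMB charter, which might settle it, is not among the documents.

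**A reader might also infer that the shortened regimen is itself undefined or faulty, because A-2 would keep an IV dose on Day 21.** The documents do not support that. Section 6.8.1 describes that infusion as "creating an in-situ vaccination step intended to create anti-tumor specific immunity", and Section 8 lists it under the same step ("The vaccination step: Subjects will receive IV AlloStim"). The steps are set out by day and route, and no IV-free aim is stated.

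**Conclusion.** The plan's quantitative safety rules contradict each other and should be corrected. The contradiction starts at the smallest possible count: one ADLT among the first three subjects (33.3%) requires both closure and expansion. The 2-of-3 consequence differs between Sections 3 and 8. The activation-or-booster exception exists only in Section 15.7.

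This rests on reading the 33% rule as written, with ADLTs counted when they occur and no unwritten minimum number.

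Three stronger readings should be avoided.

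- A reader might infer that Section 15.7 reverses the stop for any pattern of toxicity. It does so only when all DLTs fall in activation or booster, and only if the DSMB so decides.
- A reader might count discontinuation, no dosing, no escalation and shortened continuation as four competing outcomes after 2 of 3 in the second cohort. The first three are compatible, and current Part 1 has no third schedule to escalate to. The real contrast is stopping versus DSMB-approved continuation.
- A reader might attach a probability to the conflict. The documents give no ADLT rate for these schedules, so any such figure would reflect only the rate assumed.

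**What to change.** Put one rule, worded identically, in Sections 3, 8 and 15.7:

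1. The 33% discontinuation rule applies once at least six subjects have been dosed. Before that, the 3+3 ADLT rules govern. The 1-of-3 expansion can then operate, and 2 of 6 (33.3%) still closes the protocol.
2. ADLTs in two or more of three subjects mean no further dosing, as in Section 8, in both sections. State that this overrides the Section 15.7 exception. Say also whether the bar covers one schedule or the whole protocol, because below six subjects it becomes the operative stop.
3. Either copy the activation-or-booster exception into Sections 3 and 8, with its DSMB condition, or delete it from Section 15.7.

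No patients or procedures are added. The cost is a protocol amendment, which Section 17.4 makes subject to IEC/IRB approval, possible alignment of the DSMB charter, and slightly less DSMB flexibility. One consequence should be accepted openly: below six subjects, a cumulative DLT that is not an ADLT would be handled by the DSMB review that Section 15.7 already requires after any DLT, and not by the percentage rule.

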# **16. STATISTICAL METHODS**

#### **16.1.** GENERAL CONSIDERATIONS

The Phase I/IIb study is primarily designed to assess the safety and tolerability of the study drug dosing schedule and the related immune response. Any evidence of clinical objective anti-tumor activity and/or symptomatic changes will be recorded.

Safety analyses will be performed on all subjects who receive any dose of study medication. All summary data will be presented by dosing schedule (Schedule A-1 vs Schedule A-2 vs. Schedule A-3 vs. Schedule A-4 vs. Schedule B vs. Schedule C vs. Schedule D vs. Schedule E vs. Schedule F). Any evidence of clinical objective anti-tumor activity and/or symptomatic changes will be recorded.

Descriptive statistics and/or subjects' listings will be provided for demographic data, incidence of adverse events (overall, by intensity, and by relationship to study medication), incidence of clinically significant laboratory abnormalities, vital signs, medical history and physical exam, and tumor assessments.

If subjects are administered steroids, the subject data will be censored at the date of steroid administration.

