## **Brief Description of the Protocol:**

This is a single center, open label study comparing CryoVaxTM personalized anti-tumor vaccine protocol combining the cryoablation of a selected metastatic lesion with intra-lesional immunotherapy with AlloStim® alone. The treatment schedules both have the following steps: (1) priming with intradermal AlloStim®; (2) vaccination combining cryoablation with intratumoral AlloStim® or intravenous AlloStim® dosing in the place of cryoablation; (3) activation with intravenous AlloStim®; and (4) booster with intravenous AlloStim®. All subjects are followed for safety during the dosing period and until 28 days following the last dose (Safety Evaluation Period"). All subjects are continued to be followed for survival after the Safety Evaluation Period.

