## **Statistical Analysis:**

Safety analyses will be performed on the safety population, defined as all subjects in the Intent to Treat (ITT) population that received any dose of study medication. The number of AEs reported will be summarized. Subjects will be censored is still alive at data cut-off or if they withdraw consent. The incidence and percentage of subjects with at least one occurrence of a preferred term will be included, according to the most severe NCI-CTCAE Version 4.03 grade.

Causality (relationship to study drug) will be summarized separately. Duration of AE will be determined and included in the listings along with action taken and outcome.

Laboratory results will be classified according to NCI-CTCAE Version 4.03. Incidence of laboratory abnormalities will be summarized; laboratory results not corresponding to an NCI-CTCAE Version 4.03 terms will not be graded. Laboratory toxicity shifts from baseline to worst grade will also be provided.

Any clinically significant results from physical examination and vital signs measurements will be tabulated.

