# 7. STUDY OBJECTIVES

#### 7.1. PRIMARY OBJECTIVES

- 1. To determine the safety of AlloStim® combined with cryoablation vs AlloStim® alone.
- 2. Determine the schedule that provides the greatest efficacy and least adverse events

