### Dosing Schedule A-1: Intradermal and Intravenous Dosing Combined With Cryoablation

The priming step: Subjects will receive an ID injection of AlloStim® (0.5ml) on Days 0, 7, and 14 all in different locations.

The vaccination step: Subjects will receive cryoablation and intratumor (IT) injection of AlloStim® (3 ml) on Day 21.

The activation step: Subjects will receive an IV infusion of AlloStim® (3ml) on Day 28. The booster step: Subjects will receive two (optional) IV booster infusions of AlloStim® (5ml), one on Day 56 and Day 84.

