#### **16.1.3. Primary Endpoint**

Safety is the primary endpoint. AEs and SAEs will be coded, graded and summarized by attribution. Safety analysis will be performed on all subjects who receive any dose of study medication. AEs that occur after the Safety Evaluation Period will not be included in safety evaluations.

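### By-schedule adverse-event percentages ignore unequal follow-up and do not separate Part 1 from Part 2, so one schedule can look safer with no true difference

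*Combined protocol and SAP*

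**What the plan says.** The Statistical Analysis part of the Protocol Abstract defines the AE measure: "The incidence and percentage of subjects with at least one occurrence of a preferred term will be included". Section 16.1.4 likewise summarises incidence by organ class, preferred term, severity and relationship. The population in 16.1 is everyone given any dose, and "All summary data will be presented by dosing schedule".

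The observation window is individual. The Brief Description of the Protocol says "All subjects are followed for safety during the dosing period and until 28 days following the last dose", and section 16.1.3 adds that "AEs that occur after the Safety Evaluation Period will not be included in safety evaluations". No rate per unit of follow-up, time-to-event AE summary or common cut-off is planned.

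Dosing length can vary. For A-1, section 8 says "Subjects will receive two (optional) IV booster infusions". Section 11.2.1 stops treatment in subjects who deteriorate without evidence of response, and section 8 stops it after an acute dose-limiting toxicity.

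The comparison matters to the plan. Section 7.1 lists as its second primary objective: "Determine the schedule that provides the greatest efficacy and least adverse events". Section 8 has the Part 1 safety and efficacy data reviewed and "the favored schedule advanced to Part 2", where up to 25 more subjects may enter.

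**The concern.** A crude percentage compares groups fairly only if the groups are watched for similar times. Here the time watched depends on how long each subject stays on treatment, which may differ by schedule and is related to outcome. A subject dosed only on Day 0 counts fully in the denominator but contributes 28 days.

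The second issue is selection. Three subjects per schedule help decide which schedule continues, and the same subjects then appear in the by-schedule tables. If AEs influenced the decision, the dropped schedule's figures are biased upwards and the favored schedule's Part 1 figures downwards.

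At stake is the reading of a primary objective. The tables that would answer which schedule has fewer AEs can show a difference arising from follow-up length or from the selection step.

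**Working it through.** The plan gives no AE rate or window length to reproduce. Its only sample-size figure is at least 3 subjects per schedule (16.1.8), asserted without inputs. All event rates below are therefore assumptions, shown over a range.

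**Step 1: scheduled windows (day of last dose + 28; dosing days from the Protocol Abstract and section 8)**

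| Last dose | A-1 | A-2 |
|---|---|---|
| First dose only | 0 + 28 = 28 | 0 + 28 = 28 |
| Activation, no booster | 28 + 28 = 56 | 28 + 28 = 56 |
| First booster | 56 + 28 = 84 | 49 + 28 = 77 |
| Second booster | 84 + 28 = 112 | 77 + 28 = 105 |

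These are not strict limits. Death or steroid censoring (16.1) can shorten the window. Permitted delays (12.1) or further monthly boosters (14.6) can lengthen it.

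**Step 2: effect of window length, same hazard in both schedules**

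Risk over t days is F(t) = 1 − exp(−λt), with λ = −ln(1 − r)/112, where r is the assumed 112-day risk.

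| r | F(28) | F(56) | F(105) | F(112) |
|---|---|---|---|---|
| 31% | 8.8% | 16.9% | 29.3% | 30.9% |
| 50% | 15.9% | 29.3% | 47.8% | 50.0% |

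(The 31% row uses r = 0.3095.) Suppose every subject completes activation, a share q receives both boosters, and the rest receive none. The expected crude percentage is q·F(112) + (1 − q)·F(56) for A-1 and q·F(105) + (1 − q)·F(56) for A-2.

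| Boosted share, A-1 / A-2 | A-1 minus A-2, r = 31% | r = 50% |
|---|---|---|
| all / all | +1.6 points | +2.2 |
| half / half | +0.8 | +1.1 |
| half / all | −5.4 | −8.1 |
| none / all | −12.4 | −18.5 |
| all / half | +7.8 | +11.5 |

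For example, half / all at 50%: A-1 = (50.0 + 29.3)/2 = 39.6% (unrounded inputs), A-2 = 47.8%.

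**Step 3: does a rate remove this?** Under a constant hazard, expected time at risk to first event or window end w is F(w)/λ. First events divided by time at risk is then F(w) ÷ (F(w)/λ) = λ for any mix of windows. At r = 50% both schedules have a true rate of ln 2/112 = 0.619 per 100 subject-days.

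**Step 4: effect of selection**

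Assume two independent Binomial(3, p) counts with the same p, no 3+3 expansion, the schedule with fewer affected subjects favored (ties split), and 25 subjects added.

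At p = 0.30, P(X ≤ 0, 1, 2) = 0.343, 0.784, 0.973.
- Dropped schedule: E[max]/3 = [(1 − 0.343²) + (1 − 0.784²) + (1 − 0.973²)]/3 = 1.321/3 = 44.0%.
- Favored schedule, Part 1: E[min]/3 = (0.657² + 0.216² + 0.027²)/3 = 0.479/3 = 16.0%.
- Favored schedule, both Parts: (0.479 + 25 × 0.30)/28 = 28.5%.
- Gap: 44.0 − 28.5 = 15.5 points. Of this, 30.0 − 28.5 = 1.5 comes from pooling and 44.0 − 30.0 = 14.0 from the dropped schedule's own three subjects.

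The gap is 8.3 points at p = 0.10 (0.8 from pooling) and 17.3 at p = 0.50 (1.7 from pooling).

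**The case against.** The strongest reply has five parts.

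- **Pooling is not stated.** A reader might infer from the by-schedule rule that Parts 1 and 2 are to be merged. The documents do not say so. Section 8 closes the Part 1 safety evaluation as a unit and promises a safety report per cohort, 15.3.2 sends safety information to FDA at the end of Part 1, and 16.1.5 is headed as Part 2 only. This stands. What remains is that section 16 does not separate the Parts in the AE tables.
- **Selection may not rest on AEs.** Section 8 uses efficacy as well and gives no numerical rule. This stands: the 44% is the result if AE count alone decides, and the bias shrinks as efficacy takes over.
- **The direction is open.** A reader might infer that the schedule with more early stopping must look safer. A subject stopped for an acute toxicity already counts as an event, disease exacerbation is an AE (section 15), and death in the window is a serious AE (15.2). Such a schedule could look worse.
- **Constant hazard is doubtful.** Acute toxicity is assessed within 48 hours of dosing, and in the earlier study the three commonest treatment-emergent events affected 81% to 93% of subjects (6.6.1). If events cluster around doses, the figures are only indicative. The planned 7 doses in A-1 and 9 in A-2 are also a genuine schedule difference.
- **The analysis is descriptive and small.** No test between schedules is planned, one subject in three is 33 points, and AE dates are collected (15.3.3), so rates could be produced later. This limits the consequence. But a primary objective invites the comparison, and stating the measure in advance costs almost nothing.

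**Conclusion.** The point holds in a conditional form. Following the plan exactly can produce a false difference between schedules, but need not. At full dosing, or with equal booster uptake, the window effect is about 1 to 2 points. It becomes material, at 5 to 8 or 12 to 19 points, only if boosters or early stopping differ by schedule. No document says they will. It is a live possibility because section 8 marks the boosters optional for A-1 but not for A-2.

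It would be wrong to conclude that pooling the Parts creates the selection gap. Pooling supplies about 1.5 of the 15.5 points at 30% risk. The other 14.0 belong to the dropped schedule's own three subjects and remain when Part 2 is shown alone. These sizes rest on assumed event rates, a constant hazard common to both schedules, 25 Part 2 subjects and, for selection, a choice made on AE count alone.

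**What to change.** In section 16.1.4:

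- Add first-event AE rates per subject-month at risk over the Safety Evaluation Period, by schedule, beside the percentages.
- Add a cumulative incidence over a common window ending before the first booster of either schedule (Day 0 to Day 48), censoring subjects whose AE follow-up ends earlier. A Day 56 cut-off is less suitable: it would include A-2's Day 49 booster and seven days after it, but essentially no follow-up of A-1's Day 56 booster.
- Report Part 1, labelled as selection data, and Part 2 in separate columns. The label matters: in the 30% example the two Part 1 columns would be expected to read 16.0% and 44.0%.
- Take the favored schedule's AE estimate from Part 2. State that the dropped schedule's three subjects are not an unbiased comparator for either the Part 2 or the pooled data.

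The booster descriptions must be reconciled. For A-1, the Protocol Abstract and section 8 give different volumes. For A-2, the Abstract calls for three optional boosters but lists two days, while section 8 gives two and does not mark them optional.

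The cost is a few tables and no new data. The favored schedule's estimate would rest on 25 rather than 28 subjects, so its standard error grows by about 6% (√(28/25) = 1.058).
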